5.1.8 Analysis Cut-Off Dates

After the end of the dose escalation part of the trial, a full analysis for safety and PK/CCI data will be made. The primary data cut-off date for the dose escalation part is 3 months after the last subject in the dose escalation part received the first dose of MSB0011359C.

The primary data cut-off for the analysis of each expansion cohort separately will be 6 months after the last subject in that cohort started treatment.

The final data cut-off is 1 year after the last subject has received the last dose of MSB0011359C.

5.2 Discussion of Trial Design

This is a Phase I, open-label, dose escalation trial with an expansion part in cohorts of subjects with GC, ESCC, BTC and HCC. An open-label, unblinded design is appropriate for a dose escalation trial with expansion cohorts in advanced cancer subjects since subjects have exhausted treatment options.

In this trial, the assessment of the safety and tolerability of the IMP with the determination of the MTD (in the dose escalation part only) is set to be the primary objective. The determination of the MTD is one of the first major steps in the development of a compound entering early clinical development because it might be determined that the highest tolerable dose is important in future clinical development in order to achieve the best efficacy to risk ratio for subjects. The MTD will be determined using a standard "3+3 subjects" dose-escalation design based on DLT assessments, which is commonly used in first-in-man oncology trials (Crowley 2006). The aim of this design is to maximize the protection to subjects and reduce the chances of more subjects to be exposed to possible drug toxicities; however, at the end of the dose-escalation part, it is intended to fill cohorts as described in Section 5.1.1 to identify a reasonable dose for the expansion part. All these assessments will be correlated to PK parameters to potentially aid selection of the most meaningful dose for the expansion cohorts or future studies.

CONFIDENTIAL INFORMATION

A reasonably safe starting dose of 3 mg/kg has been chosen taking also into account the information from the clinical experience with the parent monoclonal antibody, avelumab, and the predicted lack of overlapping immune-related safety profile with TGFβ inhibition, as previously discussed. Initial dose setting follows the principle that the starting dose should be pharmacologically active but also reasonably safe to use. This initial dose estimation algorithm is proposed in ICH S9:

The dose to be used in the expansion part of the trial will be determined based on the data from the dose escalation part. The parameters considered for selection of the dose to be used in expansion part will include safety profile, PK, pharmacodynamics, and antitumor efficacy. In addition to determining the MTD, the trial will serve to explore biologic and clinical parameters after exposure to MSB0011359C. Due to a limited understanding of the interaction of the immune system and tumors in cancer subjects, there can be no certainty that the doses to be examined will be associated with relevant antitumor activity, although preliminary results with the parent avelumab antibody suggest promising clinical antitumor activity. The selection of the dose to be used for further clinical evaluation will be based on the best current scientific knowledge.

The target population for the dose escalation part comprises subjects with metastatic or locally advanced solid tumors who have exhausted standard treatment options. There will be 4 cohorts of subjects with GC, ESCC, BTC and HCC in the expansion part. In order to obtain a trend of biological/clinical activity, to assess target engagement based on tumor tissue samples and to collect further safety data, a treatment expansion at a meaningful dose level to be identified during the dose-escalation part to ensure further development in selected settings is justified.

The tests and analyses to examine the biologic effects of MSB0011359C dosing will include the assessment of markers of immune activation known to show typical changes after treatment with therapies blocking immune checkpoints.

5.2.1 Inclusion of Special Populations

Not applicable.

5.3 Selection of Trial Population

Only persons meeting all inclusion criteria and no exclusion criteria may be enrolled into the trial as subjects. Prior to performing any trial assessments not part of the subject's routine medical care, the Investigator will ensure that the subject has provided written informed consent following the procedure described in Section 9.2.

1

5.3.1 Inclusion Criteria

For inclusion in the trial, all of the following inclusion criteria must be fulfilled.

5.3.1.1 Inclusion Criteria for Dose Escalation

- 1. Able and willing to give written informed consent and has signed the appropriate written informed consent form (ICF), prior to performance of any trial activities.
- 2. Eligible male or female subjects aged ≥ 20 years.
- 3. Histologically or cytologically proven metastatic or locally advanced solid tumors, for which no effective standard therapy exists or standard therapy has failed.
- 4. ECOG PS of 0 to 1 at trial entry.
- 5. Life expectancy \geq 12 weeks as judged by the Investigator.
- 6. Adequate hematological function defined by white blood cell (WBC) count $\geq 3 \times 10^9/L$ with absolute neutrophil count (ANC) $\geq 1.5 \times 10^9/L$, lymphocyte count $\geq 0.5 \times 10^9/L$, platelet count $\geq 75 \times 10^9/L$, and Hgb ≥ 9 g/dL (in absence of blood transfusion).
- 7. Adequate hepatic function defined by a total bilirubin level $\leq 1.5 \times \text{ULN}$, an AST level $\leq 2.5 \times \text{ULN}$, and an ALT level $\leq 2.5 \times \text{ULN}$. For subjects with liver involvement in their tumor, AST $\leq 5.0 \times \text{ULN}$, ALT $\leq 5.0 \times \text{ULN}$, and bilirubin ≤ 3.0 is acceptable.
- 8. Adequate renal function defined by an estimated creatinine clearance > 50 mL/min according to the Cockcroft-Gault formula or by measure of creatinine clearance from 24-hour urine collection.
- 9. Highly effective contraception (that is, methods with a failure rate of less than 1% per year) for both male and female subjects if the risk of conception exists (Note: The effects of the trial treatment on the developing human fetus are unknown; thus, women of childbearing potential and men must agree to use highly effective contraception, defined in Appendix 2 or as stipulated in national or local guidelines). Highly effective contraception must be used 30 days prior to first trial treatment administration, for the duration of trial treatment, and at least for 4 months after stopping trial treatment. Should a woman become pregnant or suspect she is pregnant while she or her partner is participating in this trial, the treating physician should be informed immediately.
- 10. Woman of childbearing potential must have a negative serum pregnancy test at screening visit and a negative serum or urine pregnancy test at Day 1 before dosing, if applicable.

5.3.1.2 Inclusion Criteria for Expansion Cohorts

- 1. Able and willing to give written informed consent and has signed the appropriate written ICF, prior to performance of any trial activities.
- 2. Eligible male or female subjects aged ≥ 20 years.

CONFIDENTIAL INFORMATION

- 3. Subjects must have one of the following:
 - GC: Histologically or cytologically confirmed recurrent or refractory unresectable stage IV gastric or gastro-esophageal junctional adenocarcinoma (according to American Joint Committee on Cancer/Union Internationale Contre le Cancer 7th edition) for which no standard therapy exists or standard therapy has failed.
 - **ESCC:** Histologically or cytologically confirmed esophageal squamous cell cancer for which no standard therapy exists or standard therapy has failed.
 - BTC, second line: Histologically or cytologically confirmed biliary tract cancer. Must have failed or are intolerant to one line of systemic treatment. Patients who received adjuvant chemotherapy and had evidence of disease recurrence within 6 months of completion of the adjuvant treatment are also eligible.
 - HCC, second line or later, or sorafenib intolerant: Histologically confirmed HCC. Must be unresectable or advanced disease not amenable to curative resection. Must have had progression following at least 1 line of prior sorafenib therapy (must have received at least 14 days of sorafenib at least 400 mg per day) or previously considered to be sorafenib intolerant.

Uninfected, HCV and HBV infected subjects are eligible. Subjects infected with HBV must be treated and on a stable dose of entecavir, tenofovir, or lamivudine (adefovir or interferon not allowed) at study entry and with planned monitoring and management according to appropriate labeling guidance. Any prior HCV therapy for curative intent must be completed prior to entry; if subjects reach stable disease, CR or PR of at least 3 months duration and are considered medically stable, then HCV small molecule treatments are allowable in the judgement of the Investigator and in consultation with the Medical Monitor and following appropriate labeling guidance for initiation, monitoring, and management.

Additional inclusion criteria for HCC subjects include:

- o Child-Pugh A or B7
- o Albumin $\geq 2.8 \text{ g/dL}$
- o International normalized ratio (INR) < 1.7
- o Prothrombin time < 4 seconds over control
- \circ Hepatic function defined by a total bilirubin level \leq 3 mg/dL and AST and ALT levels \leq 5 \times ULN
- O Adequate hematological function defined by WBC count $\geq 2.5 \times 10^9/L$ with ANC $\geq 1.5 \times 10^9/L$, lymphocyte count $\geq 0.5 \times 10^9/L$, platelet count $\geq 50 \times 10^9/L$, and hemoglobin ≥ 9 g/dL (in absence of blood transfusion)
- O Subjects with no allergies to contrast and able to tolerate CT or MRI contrast in the opinion of the Investigator.

CONFIDENTIAL INFORMATION

- 4. Availability of tumor (primary or metastatic) archival material or fresh biopsies within 28 days before first administration of IMP is mandatory. If no archival material is available and only one lesion is amenable for biopsy and it is the only target lesion, the Medical Monitor should be consulted for subject eligibility). Tumor biopsies and tumor archival material must be suitable for CCI as described in the Laboratory Manual.
- 5. Disease must be measurable with at least 1 unidimensionally measurable lesion by RECIST 1.1.
- 6. ECOG PS of 0 to 1 at trial entry.
- 7. Life expectancy ≥ 12 weeks as judged by the Investigator.
- 8. For subjects with GC, ESCC, or BTC, adequate hematological function defined by WBC count $\geq 3 \times 10^9$ /L with ANC $\geq 1.5 \times 10^9$ /L, lymphocyte count $\geq 0.5 \times 10^9$ /L, platelet count $\geq 75 \times 10^9$ /L, and Hgb ≥ 9 g/dL (in absence of blood transfusion).
- 9. For subjects with GC, ESCC, or BTC, adequate hepatic function defined by a total bilirubin level \leq 1.5 \times ULN, an AST level \leq 2.5 \times ULN, and an ALT level \leq 2.5 \times ULN.
- 10. Adequate renal function defined by an estimated creatinine clearance > 50 mL/min according to the Cockcroft-Gault formula or by measure of creatinine clearance from 24-hour urine collection.
- 11. Highly effective contraception (that is, methods with a failure rate of less than 1% per year) for both male and female subjects if the risk of conception exists (Note: The effects of the trial treatment on the developing human fetus are unknown; thus, women of childbearing potential and men must agree to use highly effective contraception, defined in Appendix 2 or as stipulated in national or local guidelines). Highly effective contraception must be used 30 days prior to first trial treatment administration, for the duration of trial treatment, and at least for 4 months after stopping trial treatment. Should a woman become pregnant or suspect she is pregnant while she or her partner is participating in this trial, the treating physician should be informed immediately.
- 12. Woman of childbearing potential must have a negative serum pregnancy test at screening visit and a negative serum or urine pregnancy test at Day 1 before dosing, if applicable.

5.3.2 Exclusion Criteria

Subjects are not eligible for this trial if they fulfill any of the following exclusion criteria:

- 1. Concurrent treatment with non-permitted drugs (see Section 6.5.2).
- 2. Prior therapy with any antibody/drug targeting T cell coregulatory proteins (immune checkpoints) such as anti-PD-1, anti-PD-L1, anti-CTLA-4 antibody (consult Medical Monitor if necessary), or anti-4-1BB antibody is not allowed, inclusive of intrahepatic, localized administration of such agents.

CONFIDENTIAL 74/167

- 3. Prior therapy with any antibody/drug targeting TGFβ/TGFβ receptor.
- 4. Anticancer treatment within 21 days before the start of trial treatment, eg, cytoreductive therapy, radiotherapy involving more than 30% of the bone marrow (with the exception of palliative bone directed radiotherapy), immune therapy, or cytokine therapy.
- 5. Anticancer treatment with antibody within 28 days before the start of trial treatment.
- 6. Major surgery within 28 days before the start of trial treatment (excluding prior diagnostic biopsy).
- 7. Systemic therapy with immunosuppressive agents within 7 days before the start of trial treatment; or use of any investigational drug within 28 days before the start of trial treatment.
- 8. Previous malignant disease other than the target malignancy to be investigated in this trial with the exception of cervical carcinoma in situ and superficial or non-invasive bladder cancer (treated with curative intent) within the last 5 years or basal cell or squamous cell carcinoma in situ within the last 3 years.
- 9. Rapidly progressive disease which, in the opinion of the Investigator, may predispose to inability to tolerate treatment or trial procedures.
- 10. Subjects with active central nervous system (CNS) metastases causing clinical symptoms or metastases that require therapeutic intervention are excluded. Subjects with a history of treated CNS metastases (by surgery or radiation therapy) are not eligible unless they have fully recovered from treatment, demonstrated no progression for at least 2 months, and do not require continued steroid therapy. Subjects with CNS metastases incidentally detected during Screening which do not cause clinical symptoms and where no therapeutic intervention is needed should be discussed with the Sponsor.
- 11. Receipt of any organ transplantation, including allogeneic stem-cell transplantation, but with the exception of transplants that do not require immunosuppression (eg, corneal transplant, hair transplant).
- 12. Significant acute or chronic infections including, among others:
 - Positive test for human immunodeficiency virus (HIV) or known acquired immunodeficiency syndrome
 - Except for the HCC cohort, HBV infection (HBV surface antigen positive or HBV core antibody positive with reflex to positive HBV DNA) or HCV infection (positive HCV antibody with reflex to positive HCV RNA)
 - Subjects with active tuberculosis (history of exposure or history of positive tuberculosis test; plus presence of clinical symptoms, physical or radiographic findings)

CONFIDENTIAL 75/167

- 13. Active autoimmune disease that might deteriorate when receiving an immunostimulatory agent:
 - Subjects with diabetes type I, vitiligo, alopecia, psoriasis, hypo- or hyperthyroid disease not requiring immunosuppressive treatment are eligible.
 - Subjects requiring hormone replacement with corticosteroids are eligible if the steroids are administered only for the purpose of hormonal replacement and at doses ≤ 10 mg of prednisone or equivalent per day.
 - Administration of steroids for other conditions through a route known to result in a minimal systemic exposure (topical, intranasal, intro-ocular, or inhalation) is acceptable.
- 14. Interstitial lung disease or its history.
- 15. Known history of hypersensitivity reactions to MSB0011359C or its products, or known severe hypersensitivity reactions to monoclonal antibodies (Grade ≥ 3 NCI-CTCAE v4.03), any history of anaphylaxis, or recent, within 5 months, history of uncontrolled asthma.
- 16. Persisting toxicity (except alopecia and vitiligo) related to prior therapy Grade > 1 NCI-CTCAE v4.03; however, sensory neuropathy Grade ≤ 2 is acceptable.
- 17. Pregnancy or currently in lactation. Subject is not eligible even if lactation is suspended.
- 18. Known alcohol or drug abuse.
- 19. Clinically significant cardiovascular/cerebrovascular disease as follows: cerebral vascular accident / stroke (< 6 months prior to enrollment), myocardial infarction (< 6 months prior to enrollment), unstable angina, congestive heart failure (≥ New York Heart Association Classification Class II), or serious cardiac arrhythmia.
- 20. Clinically relevant diseases (eg, inflammatory bowel disease) and/or uncontrolled medical conditions, which, in the opinion of the Investigator, might impair the subject's tolerance or ability to participate in the trial.
- 21. Any psychiatric condition that would prohibit the understanding or rendering of informed consent.

h\//

- 22. Legal incapacity or limited legal capacity.
- 23. Vaccine administration within 4 weeks of IMP administration. Vaccination with live vaccines while on trial is prohibited. Administration of inactivated vaccines is allowed (eg, inactivated influenza vaccines).

Additional exclusion criteria for subjects in the HCC cohort include:

- 24. Any prior or current ascites that requires paracentesis for control; or history of variceal bleeding; or history of hepatic encephalopathy; or history of obstructive jaundice.
- 25. Hepatitis D virus (HDV) co-infection with HBV (if HBV surface antigen or HBV DNA positivity at Screening, then must check for HDV status).
- 26. Chemoembolization or radioembolization within 28 days prior to IMP administration.

5.4 Criteria for Initiation of Trial Treatment

The inclusion and exclusion criteria will be checked at the Screening visit. Eligible subjects will be enrolled before treatment start after verification of fulfilling all inclusion criteria without matching any exclusion criterion.

5.5 Criteria for Subject Withdrawal

5.5.1 Withdrawal from Trial Treatment

Subjects will be withdrawn from trial treatment for any of the following reasons:

- Confirmed PD per RECIST 1.1: Subjects should continue treatment beyond the initial determination of PD, through their next tumor assessment, provided:
- a. There are no new Grade 2 or greater symptoms or significant worsening of existing symptoms.
- b. There is no decrease in ECOG PS.
- c. In the opinion of the Investigator, the subject does not require new anticancer therapy.
 - Subjects should be discontinued from treatment thereafter if further evidence of PD; however, continued treatment is possible in consultation with the Medical Monitor.
 - Occurrence of an exclusion criterion, which is clinically relevant and affects the subject's safety, if discontinuation is considered necessary by the Investigator and/or Sponsor.
 - Therapeutic failure requiring urgent additional cancer therapy.
 - Occurrence of any Grade \geq 3 ADRs or repetitive Grade 2 ADRs as defined in Section 5.1.7.2.
 - Occurrence of AEs, at the Investigator's discretion.

CONFIDENTIAL INFORMATION

- Pregnancy.
- Use of prohibited concomitant drug, as defined in Section 6.5.2, where the predefined consequence is withdrawal from the IMP.
- Non-adherence/noncompliance to the trial protocol or trial requirements (see Section 6.9).
- Withdrawal of consent.
- Participation in any other trial.

For subjects who miss ≥ 2 consecutive doses for medical reasons, the Medical Monitor should be consulted.

Subject Replacement

For the dose escalation part, subjects with the following events during the DLT observation period (see Section 5.1.3.3 and Section 5.5.2) will be considered non-completers and have to be replaced:

- Deviation in MSB0011359C administration of greater than -3 days or +1 day due to reasons other than DLT.
- Other condition that DLT is not evaluable (eg, use of non-permitted medicines as detailed in Section 6.5.2).

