5.1.3.3 Dose-Limiting Toxicity

A DLT is defined as any Grade \geq 3 AE, with the exceptions described hereafter, assessed as related to IMP by the Investigator and/or Sponsor (ie, Grade \geq 3 adverse drug reaction [ADR]; grading

CONFIDENTIAL INFORMATION

according to the National Cancer Institute (NCI) Common Terminology Criteria for Adverse Events Version 4.03 [CTCAE v4.03]) occurring in the DLT evaluation period (21 days after first administration of MSB0011359C) confirmed by the SMC to be relevant for the IMP treatment. The SMC recognizes that in the absence of prior human experience with MSB0011359C, a conservative approach will be adopted in ascribing the relevance of the treatment-related toxicity to IMP. Treatment-related SAEs will be ascribed as related to drug except where a clear relationship to the underlying disease or recognized comorbidities is evident.

A DLT is defined as the following:

Any Grade \geq 3 AE that is related to MSB0011359C, occurring during the DLT evaluation period (21 days after administration of MSB0011359C), **except** for those listed below. Also, elevated alanine aminotransferase (ALT) or aspartate aminotransferase (AST) 3 times the upper limit of normal (ULN) and a concomitant elevation of bilirubin 2 times the ULN attributable to study drug constitutes a DLT.

- Grade 3 infusion-related reactions resolving within 6 hours from the end of infusion and controlled with medical management.
- Transient (≤ 6 hours) Grade 3 flu-like symptoms or fever, which is controlled with medical management.
- Transient (≤ 24 hours) Grade 3 fatigue, local reactions, headache, nausea, emesis that resolves to Grade < 1.
- Any Grade ≥ 3 drug-related amylase or lipase abnormality that is not associated with symptoms or clinical manifestations of pancreatitis.
- Grade 3 Hgb decrease (< 8.0 g/dL) that resolves to at least 9 g/dL within 14 days or the changes in the associated RBC parameters resolve within 14 days without blood transfusion or erythroid growth factor use.
- Malignant skin lesion that is local and can be resected with negative resection margin.

Dose-limiting toxicities that require treatment discontinuation are described in Section 5.1.7.2.

Subjects who do not complete the DLT observation period for reasons other than a DLT will be replaced.

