5.5.2 Withdrawal from the Trial

Subjects may withdraw from the trial at any time without giving a reason. Withdrawal of consent will be considered withdrawal from the trial.

A subject must be withdrawn in the event of any of the following:

- Withdrawal of the subject's consent.
- Participation in any other therapeutic trial during the treatment duration of this trial; however, subjects will continue to be followed for survival.

If a subject has failed to attend scheduled trial assessments, the Investigator must determine and record the reasons and the circumstances as completely and accurately as possible.

In case of withdrawal from the trial, the assessments scheduled for the last visit (End-of-Treatment visit) should be performed (see Section 7.1.4), if possible, with focus on the most relevant assessments. In any case, the appropriate End-of-Treatment electronic case report form (eCRF) visit must be completed. In case of withdrawal, subjects will be asked to continue safety and survival follow-up, which includes the collection of data on survival and subsequent anticancer therapy. After completion of the Follow-up period or after the End-of-Treatment visit, whatever is applicable, the appropriate eCRF section for Trial Termination must be completed.

CONFIDENTIAL INFORMATION

If a subject is withdrawn prior to disease progression for any reason in the expansion part of the trial, the subject will not be replaced. For the dose escalation part, subjects with the following events during the DLT observation period will be considered non-completers and have to be replaced: 1) deviation in MSB0011359C administration of greater than -3 days or +1 day due to reasons other than DLT; or 2) other condition that DLT is not evaluable (eg, use of non-permitted medicines).

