6.5.2 Prohibited Medicines

As stated for the exclusion criteria in Section 5.3.2, subjects must not have had chemotherapy, radiotherapy involving more than 30% of the bone marrow (other than palliative bone directed radiotherapy as described in Section 6.5.1) within 21 days before the start of trial treatment, and anticancer treatment with antibody, major surgery, or received another investigational agent within 28 days before the start of trial treatment.

The following treatments must not be administered during the trial:

- Immunotherapy, immunosuppressive drugs (eg, chemotherapy or systemic corticosteroids except for short-term treatment of allergic reactions, endocrine replacement therapy at low dose prednisone [≤ 10 mg daily] or equivalent, or for the treatment of irAEs or other appropriate short-term steroid use), or other experimental pharmaceutical products. Short-term administration of systemic steroid or other immunosuppressant such as infliximab or mycophenolate (ie, for allergic reactions or the management of irAEs) is allowed. Steroids with no or minimal systemic effect (topical, inhalation) are allowed.
- Adefovir.
- Prophylactic use of corticosteroids for infusion-related reactions is prohibited.
- Any live vaccine therapies for the prevention of infectious disease. Administration of inactivated vaccines is allowed (eg, inactivated influenza vaccines).
- Blood transfusions and erythroid growth factors are not allowed during the 21-day DLT window during the escalation part.

CONFIDENTIAL 83/167

If the administration of a non-permitted concomitant drug becomes necessary during the trial, the subject will be withdrawn from trial treatment (the Medical Monitor may be contacted to discuss whether the IMP must be discontinued).

Medications other than those specifically excluded in this trial (as outlined in this section) may be administered for the management of symptoms associated with the administration of MSB0011359C as required. These might include analgesics, antiemetics, antihistamines, diuretics, anti-anxiety medications, and medication for pain management, including narcotic agents.

Any additional concomitant therapy that becomes necessary during the trial and any change to concomitant drugs must be recorded in the corresponding section of the eCRF, noting the name, dose, duration, and indication of each drug.

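### The second replacement rule in Protocol 5.5.1 and 5.5.2 conflicts with the DLT definition when a related hemoglobin decrease is transfused in the DLT window

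*Protocol*

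**What the plan says.** - **Replacement (Protocol 5.5.1, Subject Replacement).** Escalation subjects with either of two events in the DLT observation period "will be considered non-completers and have to be replaced". The first event is "Deviation in MSB0011359C administration of greater than -3 days or +1 day due to reasons other than DLT". The second is "Other condition that DLT is not evaluable (eg, use of non-permitted medicines as detailed in Section 6.5.2". Section 5.5.2 repeats the second as "other condition that DLT is not evaluable (eg, use of non-permitted medicines". Only the first item excludes causes that are themselves DLTs.
- **Non-permitted treatments (Protocol 6.5.2).** "Blood transfusions and erythroid growth factors are not allowed during the 21-day DLT window during the escalation part". SAP Appendix 1 (PDEV44) codes a breach of this as a non-permitted concomitant medication. Section 6.5.2 also states a consequence: "If the administration of a non-permitted concomitant drug becomes necessary during the trial, the subject will be withdrawn from trial treatment".
- **DLT definition (Protocol 5.1.3.3).** A related Grade 3 or higher event in the 21-day window is a DLT unless an exception applies. The hemoglobin exception covers a Grade 3 decrease that recovers to 9 g/dL within 14 days, or whose associated red-cell changes resolve "within 14 days without blood transfusion or erythroid growth factor use". The section's closing sentence replaces non-completers only where something other than a DLT was the cause.
- **Anemia management (Protocol 6.5.4.4).** Investigators are told to consider transfusion, particularly when hemoglobin is below 7 g/dL.

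**The concern.** One act, transfusing a subject for a drug-related hemoglobin decrease in the DLT window, has two opposite consequences. Under 5.1.3.3 it takes the event out of the exception, so the event is a DLT. Under the second replacement item it is the named example of a case that cannot be evaluated, and the subject must be replaced. The example is not far-fetched: a transfusion does hide whether hemoglobin would have recovered within 14 days, so a reader could well think the item was written for this case.

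DLT occurrence is a primary endpoint, anemia is a listed important risk (Protocol 3.4), and each dose decision rests on 3 to 6 subjects. Any effect of literal application runs one way, towards a dose looking safer than it is.

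**Working it through.** **Text, step by step.**

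1. A related Grade 3 hemoglobin decrease occurs in the window and is transfused. The no-transfusion condition in 5.1.3.3 most naturally governs both limbs of the exception, so the exception is lost and the event is a DLT. Section 6.5.4.4 uses similar wording for permanent withdrawal. Section 5.1.7.2 tolerates transfusion-managed anemia in general but sets a stricter rule inside the DLT period. The grammar would also allow the condition to attach only to the red-cell limb.
2. Transfusion in the window is on the 6.5.2 list, and the SAP codes it as a non-permitted medication.
3. Use of a 6.5.2 treatment is the stated example in the second replacement item, and replacement is mandatory.
4. That item has no exemption for a subject who has had a DLT.

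**Effect on one cohort.** The plan's maximum of 18 evaluable escalation subjects reproduces as 3 dose levels × 6. Take 3 subjects with two DLTs, one a transfused Grade 3 decrease. Counted, 2 of 3 bars escalation. If that subject is replaced by one without a DLT, the count is 1 of 3, the cohort expands to 6, and 1 of 6 meets the MTD standard.

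**Illustration.** The documents give none of these rates; all are assumed. Let p be the true DLT rate, f the share of DLTs that are transfused hemoglobin events, and r the fraction of those replaced. Among subjects kept, the DLT rate is

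q = p(1 − fr) / (1 − pfr).

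Clearing for escalation (0 of 3, or 1 of 3 then 0 of the next 3): (1 − q)³ + 3q(1 − q)⁵.

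MTD standard (at most 1 of 6): (1 − q)⁶ + 6q(1 − q)⁵.

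With p = 0.30, f = 0.20 and r = 1: q = 0.24/0.94 = 0.2553, giving 0.588 and 0.521. With r = 0: q = 0.30, giving 0.494 and 0.420.

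| p | f | Outcome | r = 0 | r = 0.5 | r = 1 |
|---|---|---|---|---|---|
| 0.30 | 0.20 | escalate | 0.494 | 0.539 | 0.588 |
| 0.30 | 0.20 | MTD standard | 0.420 | 0.468 | 0.521 |
| 0.30 | 0.10 | escalate | 0.494 | 0.516 | 0.539 |
| 0.30 | 0.10 | MTD standard | 0.420 | 0.444 | 0.468 |
| 0.20 | 0.20 | escalate | 0.709 | 0.744 | 0.780 |
| 0.40 | 0.20 | escalate | 0.309 | 0.351 | 0.401 |

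At p = 0.30 and f = 0.20, the chance of at least one such event among the first 3 subjects is 1 − (1 − 0.06)³ = 0.169.

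**The case against.** The strongest reply is that the protocol, read as a whole, already keeps the event.

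- The operative condition in the second item is that DLT cannot be evaluated, and medicine use is only an example. A subject with an observed DLT has been evaluated.
- Section 5.5.1 points to 5.1.3.3, whose closing sentence limits replacement generally.
- Under 5.1.7.2 the hemoglobin event itself requires stopping treatment. That fits the DLT analysis set in 8.4, which keeps subjects who stopped because of a DLT. A subject whose event follows the Day 15 dose may also qualify as having received every dose in the window.
- The SMC reviews all treated subjects, including non-completers (2.2.1), decides which events are DLTs, and takes a conservative approach (5.1.3.3).

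Most of this stands. It shows that counting the event is the better reading and the likely outcome. It does not remove the conflict. The example chosen for non-evaluability is the very treatment that makes the event a DLT, and the exemption was written into one item and not the next. Section 5.5.1 also lists "Use of prohibited concomitant drug, as defined in Section 6.5.2, where the predefined consequence is withdrawal from the IMP" as a withdrawal reason separate from adverse drug reactions, so which reason is recorded for such a subject is left open.

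A reader might infer that the plan as written necessarily loses these DLTs, or that the dose taken forward rested on a count with one removed. The documents support neither. The conflicting clauses mostly point to counting, and nothing shows that any subject was replaced this way.

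**Conclusion.** There is a genuine inconsistency in the rule for counting a primary endpoint, and it is minor. If the SMC counts the event, as is probable, r is 0 and nothing changes. If the replacement item is applied literally to every such event, the assumed scenarios above raise the chance of clearing a cohort by about 5 to 10 percentage points. Those figures depend wholly on assumed values of p, f and r, and on the natural reading of the no-transfusion condition. They show direction and rough scale only. The last participant in the trial started on 24 August 2017 (SAP 4), so the point matters for a clear record of the DLT rule and for any reuse of the wording. Confidence is medium, because the grammar of the exception leaves room for another reading.

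**What to change.** 1. In 5.5.1 and 5.5.2, limit the second replacement item to subjects who have not had a DLT, to match the first.
2. In 5.1.3.3, add one sentence: a related Grade 3 or higher hemoglobin decrease treated with transfusion or erythroid growth factor in the DLT window counts as a DLT, and the subject is not replaced.

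The cost is a qualifier in two places and one sentence, with no new data or subjects. The second change is more than editorial. It settles the open grammar of the exception in the conservative direction, so the clinical team should own it. Its downside is that an occasional anemia that would have recovered without transfusion is counted as a DLT. Section 6.5.2 needs no change, since it and 6.5.4.4 already provide for a transfusion that becomes necessary.
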